6.3 Rationale for Study Design and Selection of Dose

COVID-19 is a serious infectious disease that affected more than 11,190,000 people worldwide in 2020 ([Worldometer 2020](#)). There are currently no approved treatments for mild to moderate COVID-19 disease.

The dose of TQ selected for this study is consistent with the current label. Pharmacokinetic modeling suggests unbound lung concentrations at this dose exceed the EC₉₀ of tafenoquine against SARS-CoV-2 in cell culture studies [see [Section 3.4](#)]. Double-blind procedures are included to reduce bias. A placebo control is included to demonstrate the effect of treatment with TQ.

7 SELECTION AND WITHDRAWAL OF PATIENTS

7.1 Inclusion Criteria

To be eligible to participate in this study, all of the following criteria must be met:

- (1) Male or female, aged ≥ 18 years of age
- (2) Laboratory confirmed infection with SARS-CoV-2 virus by an FDA-authorized RT-PCR test
- (3) Able and willing to give written informed consent;
- (4) Willing to keep a study diary from Study Day 1 to Day 12 [± 1 day] and have daily phone or videoconferences with study team personnel
- (5) At least one of the following clinical symptoms of COVID-19 infection within the 4 days prior to and inclusive of the day of screening:
 - (i) Respiratory rate ≥ 24 /min;
 - (ii) New cough or shortness of breath that has presented within the last 4 days; and/or
 - (iii) Fever $\geq 37.7^{\circ}\text{C}$ (oral or skin surface by infrared)
- (6) Must agree not to enroll in another study of an investigational agent prior to completion of Day 28 of the study;
- (7) Able to take ARAKODA or KODATEF according to Prescribing Information
- (8) Have been symptomatic no longer than 5 days when the first dose of study medication is administered
- (9) If female, agree to use an acceptable method of birth control from the time of consent through 56 days after the last dose of study drug

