Participant Selection:	
Inclusion criteria:
 
(1) Male or female, aged ≥ 18 years of age;(2) Laboratory confirmed infection with COVID-19 virus by an FDA-authorized SARS-CoV-2 RT-PCR;(3) Able and willing to give written informed consent.(4) Willing to keep an electronic diary from Study Day 1 to Day 12 [± 1 day] and have daily phone or videoconferences with study team personnel.(5) At least one of the following clinical symptoms of COVID-19 infection within the 4 days prior to and inclusive of the day of screening:
a. Respiratory rate ≥ 24/min;b. New cough or shortness of breath that has presented within the last 4 days;c. Fever – temperature $\geq 37.7^{\circ}\text{C}$ [oral or skin surface](6) Must agree not to enroll in another study of an investigational agent prior to completion of Day 28 of the study.(7) Able to take ARAKODA or KODATEF according to Prescribing Information(8) Have been symptomatic no longer than 5 days when the first dose of study medication is administered.(9) If female, agree to use an acceptable method of birth control from the time of consent through 56 days after the last dose of study drug. 
Exclusion criteria:
 
(1) Have of the contraindications for ARAKODA or KODATEF in the prescribing information (Section 15.1) including:
a. G6PD deficiencyb. Breastfeedingc. Psychotic disorder or current psychotic symptomsd. Known hypersensitivity reaction to TQ(2) Evidence of severe or critical illness, defined by at least one of the following:
a. Clinical signs indicative of severe systemic illness with COVID-19, such as respiratory rate ≥ 30 breaths per minute, heart rate ≥ 125 beats per minute, $\text{SpO}_2 \leq 93\%$ on room airb. Respiratory failure defined based on resource utilization requiring at least one of the following:
i. Endotracheal intubation and mechanical ventilation, oxygen delivered by high flow nasal cannula (heated, humidified, oxygen delivered via reinforced nasal cannula at flow rates > 20 L/min with fraction of delivered oxygen ≥ 0.5), noninvasive positive pressure ventilation, extracorporeal membrane oxygenation (ECMO), or clinical diagnosis of respiratory failure (i.e., clinical need for one of the preceding therapies, but preceding therapies not able to be administered in setting of resource limitation)ii. Shock (defined by systolic blood pressure < 90 mmHg, or diastolic blood pressure < 60 mmHg or requiring vasopressors)iii. Multi-organ dysfunction/failure(3) Any other clinically significant acute illness unrelated to COVID-19 within seven days prior to first study drug administration

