6.2 Schedule of Study Assessments

Table 1 Schedule of Procedures

Procedure	Screening Day -4 to -1	Day 1	Day 1	Days 2 and 3 ± 1 day	Days 4 to 9	Day 10 ± 1 day	Day 11	Day 12 ± 1 day	Day 28 ± 1 day
Clinic Visit #	1	If in clinic	If at home					2 or 3	
Informed consent	X								
Eligibility criteria	X	X	X						
Pregnancy testing ¹	X							X	
Demography	X								
Medical history	X	updated	updated						
G6PD test	X								
Physical exam	X							X	
Vital signs ²	X							X	
Clinical symptoms of COVID-19 ³									
Temperature ⁴	X	X	Self-measured by patient daily and recorded in eDiary					X	
Respiration rate ⁵	X	X	Self-measured by patient daily and recorded in eDiary						
Shortness of breath (severity scale) ⁶	X	X	Self-reported by patient daily and recorded in eDiary					X	
Cough (severity scale) ⁷	X	X	Self-reported by patient daily and recorded in eDiary					X	
Pulse oximetry for oxygen saturation	X	X	Self-measured by patient daily and recorded in eDiary					X	
Prior and concomitant medications ⁸	X	updated	Recorded by clinician at telemedicine visit					X	Recorded by clinician at telemedicine visit
Adverse events			Self-reported by patient and recorded in eDiary, and recorded during telemedicine visit including severity and relationship to study drug, plus actions taken to treat AE or if drug discontinued					X	Recorded by clinician at telemedicine visit

Procedure	Screening Day -4 to -1	Day 1	Day 1	Days 2 and 3 ± 1 day	Days 4 to 9	Day 10 ± 1 day	Day 11	Day 12 ± 1 day	Day 28 ± 1 day
Clinic Visit #	1	If in clinic	If at home					2 or 3	
RT-PCR	X							X	
Hematology ⁹	X							X	
Blood chemistry ¹⁰	X							X	
Randomization		X	X						
Load eDiary to Patient Device, provide pulse ox device, thermometer, and instructions for use		X	X						
Dispense study drug ¹¹		X	X						
Study drug administration			X	Each day		X			
Medication compliance			eDiary	eDiary		eDiary			
Final drug accountability								X	

¹ A serum pregnancy test will be performed at screening and a urine or serum pregnancy test will be performed at Day 12.

² Vital signs include blood pressure and heart rate

³ COVID-19 symptoms will be assessed by designated clinical staff at in-clinic visits and will be checked at home by the patients and reported by the patient in the electronic diary (eDiary). Once the data is recorded in the diary it will be uploaded to the study database for clinician review.

⁴ Temperatures will be taken orally or on the skin surface and recorded in degrees Centigrade.

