10.1.3.2 Adverse Event and Serious Adverse Event Reporting Procedures

- Safety Contact Information:

Drug Safety Navigator (DSN)

Email: [contact]

- AE Reporting:

AEs occurring (initial occurrence or a worsening of a pre-existing condition) after the subject signs the informed consent form and up to the final follow-up visit at Day 28 will be reported and included in the study database.

AEs will be reported on the AE CRF Form, and any related questions should be directed to DSN.

- SAE Reporting:

Any SAE experienced from the time the subject signs the informed consent up to the final follow-up visit at Day 28 will be reported to DSN as described below. Additionally, SAEs that occur after completion of the Follow-up period will also be reported to DSN if the Investigator considers the SAE related to study drug.

SAEs must be reported to DSN within 24 hours of the Investigator's (site's) awareness or notification of the event. To report the SAE, the site must complete the SAE Form for the study. This form is not part of the eCRF and will be provided separately to the Investigator by DSN. Initial and follow-up

SAE reports will be sent to DSN via email to [contact], and to the sponsor's Chief Medical Officer and to the Medical Monitor.

The SAE reporting should not be delayed, and the sites may call and provide the available SAE information within 24 hours of Investigator's awareness. A written SAE Form should be sent via email to [contact], as soon as possible.

The Investigators should make every effort to provide complete information on the SAE Form. At the minimum, the initial SAE report must contain the subject's identifiers, event term as known, SAE criterion and the Investigator's causality assessment. Additional information (or updates to the previously reported information) may be provided, as it becomes available through a follow-up SAE report.

The Investigator must continue to follow the subject until the SAE resolves, the condition becomes chronic in nature, stabilizes (in the case of persistent impairment), or the subject dies. Within 24 hours of receipt of follow-up information, the Investigator must complete the SAE Form and submit any supporting documentation, as necessary (e.g., laboratory test reports, subject discharge summary, or autopsy reports) to DSN via email to [contact].

The Investigator is also required to submit SAE reports to the IRB in accordance with applicable requirements.

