10.2 Pregnancy and Birth Control

All females should use an acceptable method of birth control (to be recorded on a source document and eCRF). Since a fetus would have an unknown G6PD status, TQ should not be used in pregnant women or in lactating mothers with infants of deficient or unknown G6PD status. If a patient becomes pregnant during the study or within 56 days of discontinuing study medication, the Investigator should report the pregnancy to Medical Monitor within 24 hours of being notified. CRO personnel will then forward the Exposure In Utero form to the Investigator for completion.

The patient should be followed by the Investigator until completion of the pregnancy. If the pregnancy ends for any reason before the anticipated date, the Investigator should notify the Medical Monitor. At the completion of the pregnancy, the Investigator will document the outcome of the pregnancy. If the outcome of the pregnancy meets the criteria for immediate classification as an SAE (i.e., spontaneous abortion, stillbirth, neonatal death, or congenital anomaly), the Investigator should follow the procedures for reporting an SAE.

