5.2 G6PD Deficiency in Pregnancy and Lactation

Potential Harm to the Fetus

The use of ARAKODA during pregnancy may cause hemolytic anemia in a G6PD-deficient fetus. Even if a pregnant woman has normal levels of G6PD, the fetus could be G6PD deficient. Advise females of reproductive potential that treatment with ARAKODA during pregnancy is not recommended and to avoid pregnancy or use effective contraception during treatment and for 3 months after the last dose of ARAKODA. If a pregnancy is detected during ARAKODA use, discontinue ARAKODA as soon as possible and switch to an alternative prophylactic drug for malaria during pregnancy [*see Use in Specific Populations (8.1 and 8.3)*].

Potential Harm to the Breastfeeding Infant

A G6PD-deficient infant may be at risk for hemolytic anemia from exposure to ARAKODA through breast milk. Infant G6PD status should be checked before breastfeeding begins. ARAKODA is contraindicated in breastfeeding women when the infant is found to be G6PD deficient or the G6PD status of the infant is unknown [*see Contraindications (4)*]. Advise the woman with a G6PD-deficient infant or if the G6PD status of the infant is unknown not to breastfeed during treatment with ARAKODA and for 3 months after the final dose [*see Use in Specific Populations (8.2)*].

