8.3 Females and Males of Reproductive Potential

Pregnancy Testing

Verify the pregnancy status in females of reproductive potential prior to initiating treatment with ARAKODA. [*see Dosage and Administration (2.2), Warnings and Precautions, (5.2), and Use in Specific Populations (8.1)*].

Contraception

ARAKODA may cause hemolytic anemia in a G6PD-deficient fetus [*see Warnings and Precautions (5.2), Use in Specific Populations (8.1)*]. Advise females of reproductive potential that treatment with ARAKODA during pregnancy is not recommended and to avoid pregnancy or use effective contraception for 3 months after the final dose of ARAKODA.

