17 PATIENT COUNSELING INFORMATION

Advise the patient to read the FDA-approved patient labeling (Medication Guide).

G6PD Testing and Hemolytic Anemia

Inform patients of the need for testing for G6PD deficiency before starting ARAKODA. Advise patients on the symptoms of hemolytic anemia and instruct them to seek medical advice promptly if such symptoms occur. Patients should contact their health care provider if they have darker lips or urine as these may be signs of hemolysis or methemoglobinemia [see *Warnings and Precautions (5.1)*].

Important Administration Instructions

- Advise patients to take ARAKODA with food.
- Advise patients to swallow the tablet whole and not to break, crush or chew it.
- Advise patients to complete the full course of ARAKODA including the loading dose, maintenance dose and terminal dose.

Potential Harm to the Fetus

Advise females of reproductive potential of the potential risk of ARAKODA to a fetus and to inform their healthcare provider of a known or suspected pregnancy [see *Warnings and Precautions (5.2) and Use in Specific Populations 8.1*].

Advise females of reproductive potential to avoid pregnancy or use effective contraception during treatment with ARAKODA and for 3 months after the final dose [see *Use in Specific Populations (8.3)*].

Lactation

Advise women with a G6PD-deficient infant, or if they do not know the G6PD status of their infant, not to breastfeed during treatment with ARAKODA and for 3 months after the final dose [*see Contraindication (4), Warnings and Precautions (5.2), Use in Specific Populations (8.2)*].

Methemoglobinemia

Inform patients that methemoglobinemia has occurred with ARAKODA. Advise patients on the symptoms of methemoglobinemia and instruct them to seek medical advice promptly if such symptoms occur [*see Warnings and Precautions (5.3)*].

Psychiatric Symptoms

Advise patients who experience hallucinations, delusions, or confused thinking while taking ARAKODA to seek medical attention as soon as possible. Other psychiatric symptoms, such as changes in mood, anxiety, insomnia, and nightmares, should be promptly evaluated by a medical professional if they last more than three days or severe [*see Warnings and Precautions (5.4)*].

Hypersensitivity Reactions

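### Contraception is required for only 56 days after the last dose, while the label in the protocol's own Appendix A advises 3 months, and no reason is given for the shorter period

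*Combined protocol and SAP*

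**What the plan says.** Section 7.1, criterion 9, applies to every female participant, who must "agree to use an acceptable method of birth control from the time of consent through 56 days after the last dose of study drug". The synopsis has the same rule: "acceptable method of birth control from the time of consent through 56 days after the last dose of study drug". Section 10.2 uses the same length for notification. The investigator must tell the Medical Monitor of a pregnancy that occurs in the study or "within 56 days of discontinuing study medication", and must then follow it to its end.

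Appendix A (Section 15.1) reproduces the ARAKODA prescribing information, which gives a longer period in three places. Women of reproductive potential are to be advised:

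- label section 5.2: "to avoid pregnancy or use effective contraception during treatment and for 3 months after the last dose of ARAKODA"
- label section 8.3: "avoid pregnancy or use effective contraception for 3 months after the final dose of ARAKODA"
- label section 17: "avoid pregnancy or use effective contraception during treatment with ARAKODA and for 3 months after the final dose"

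On monitoring, footnote 1 of Table 1 (Section 6.2) states: "A serum pregnancy test will be performed at screening and a urine or serum pregnancy test will be performed at Day 12". The last planned contact is the Day 28 call.

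**The concern.** The protocol sets a shorter period than the label it attaches, against the same hazard. Section 10.2 gives the unknown G6PD status of a fetus as the reason to keep the drug from pregnant women. Label section 5.2 describes hemolysis in a fetus lacking the enzyme and notes that a mother with normal G6PD can carry such a fetus. Screening the mother therefore does not remove the risk.

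Nothing scheduled later makes up for a short written period. The last pregnancy test comes about 2 days after the final dose and the last contact about 18 days after it. From then on, the protocol's protection is the period to which the woman agreed. If it is too short, a participant can follow the protocol fully, conceive while the label still advises against it, and fall outside required notification.

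**Working it through.** **Comparing the texts.** The 56-day figure occurs in three places: synopsis criterion 9, Section 7.1 criterion 9 and Section 10.2. None gives a derivation or refers to the label's 3 months, so there is no calculation in the plan to reproduce. The label counts its 3 months from the last dose, without regard to course length, and Section 6.3 describes the trial dose as in line with the label. The two periods do not exclude each other, since 56 days is a minimum, but meeting that minimum exactly falls short of the label.

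The label sets no period for notifying pregnancies. The Section 10.2 window is short only by consequence: it closes while the label's contraception period is still running.

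**Size of the gap.** Taking 3 months as 90 to 92 days:

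- 90 − 56 = 34 days; 92 − 56 = 36 days.
- With the last dose on Day 10, criterion 9 ends at 10 + 56 = Day 66. The label period ends at 10 + 90 = Day 100 to 10 + 92 = Day 102.
- Last pregnancy test: 12 − 10 = 2 days after the last dose. Last contact: 28 − 10 = 18 days after it. If the ±1 day windows on both the dose and the visit are used, these become 0 to 4 days and 16 to 20 days.

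**Drug remaining.** Half-life inputs are 16.5 days with range 10.8 to 27.3 (Section 3.3.2.3), about 14 days (Section 3.2) and about 17 days (label section 5.6). As a consistency check, the clearance of 4.2 L/hr and volume of 2470 L in Section 3.3.2.3 give ln 2 × 2470 / 4.2 = 408 hours = 17.0 days, in line with the 16.5 to 17 day figures.

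Assuming first-order elimination, the fraction remaining after t days is 0.5^(t / half-life). For 16.5 days: 56 / 16.5 = 3.39 half-lives, and 0.5^3.39 = 9.5%; 91 / 16.5 = 5.52 half-lives, and 0.5^5.52 = 2.2%.

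| Half-life (days) | Remaining at 56 days | Remaining at 91 days |
|---|---|---|
| 10.8 (shortest) | 2.7% | 0.3% |
| 14 | 6.25% | 1.1% |
| 16.5 (mean) | 9.5% | 2.2% |
| 17 | 10.2% | 2.5% |
| 27.3 (longest) | 24.1% | 9.9% |

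Fifty-six days is exactly four half-lives at 14 days, which may be where it came from. The protocol does not say so, and its own pharmacokinetic section gives 16.5 days.

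**The case against.** Several points can be made for the plan as written.

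- Criterion 7 requires that patients be able to take the drug as its label directs, and investigators hold the label. They may well counsel women to the 3-month period. But criterion 7 sets no contraception period, and criterion 9 sets an explicit shorter one that sites will follow.
- The consent pages, the Investigator's Brochure and the KODATEF prescribing information are not in the reviewed file, so a reason for 56 days could be recorded there. This stands as a limit: no reason appears in what was reviewed. It does not alter the rule the protocol states.
- The label text is advice, while criterion 9 is mandatory. The protocol is stricter than the label elsewhere: it excludes all breastfeeding women and repeats the pregnancy test on Day 12. That is true, but neither measure covers the weeks after day 56.
- Harm requires assignment to tafenoquine, conception in a window of about five weeks, and a fetus lacking G6PD. No fetal-risk threshold is given, so the absolute risk may be small. This also stands, and the percentages above describe exposure only. Without a threshold, though, nothing supports going below the label period.
- Serious outcomes would still surface. Section 10.1.3.2 says "SAEs that occur after completion of the Follow-up period will also be reported to DSN" when the investigator considers them drug-related, and Section 10.2 sends pregnancy losses, neonatal deaths and birth defects to SAE reporting. This is a real safeguard, but it acts after exposure and depends on the site learning of the event.
- A longer notification window without a contact after Day 28 still relies on women reporting themselves. That is fair, and equally true of the present 56 days.

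**Conclusion.** The concern holds. The contraception period is wrong as written: it is 34 to 36 days shorter than the one in the label the protocol attaches, for the same stated hazard, with no justification in the reviewed text. What is lost is fetal protection over that interval, together with routine notification and follow-up of pregnancies that begin in it.

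The comparison of periods needs no assumption beyond reading 3 months as 90 to 92 days. The residual-drug figures assume first-order elimination at the stated half-lives. They illustrate exposure and do not measure fetal risk. Randomization, endpoints, power and analysis are unaffected.

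A separate background discrepancy is worth correcting, though the conclusion does not depend on it. Section 3.3.1 reports no adverse findings on fertility or embryofetal development. Label section 8.1 reports abortions in rabbits, both with and without toxicity in the mother, from about 0.4 times clinical exposure. Label section 13.1 reports fewer viable fetuses, implantations and corpora lutea in rats at 15 mg/kg, a maternally toxic dose. The label also reports no malformations in either species and no fetotoxicity in the rat embryofetal study, and it does not contradict the statement on post-natal survival.

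**What to change.** Replace 56 days with 3 months after the last dose in three places: synopsis inclusion criterion 9, Section 7.1 criterion 9, and the notification window in Section 10.2. Check that the consent form gives the same period.

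As a secondary correction, revise the Section 3.3.1 sentence to agree with label sections 8.1 and 13.1. It should report the rabbit abortions and the rat fertility findings at a maternally toxic dose, along with the absence of malformations and of rat fetotoxicity.

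The cost is wording in three places and one background sentence, plus consent text if it differs. Women commit to 34 to 36 more days of contraception, and the notification window lengthens by the same amount. No visits, tests or patients are added.

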7.2 Exclusion Criteria

Patients are not permitted to enroll in the study if any of the following criteria is met:

- (1) Have any of the contraindications for ARAKODA or KODATEF in the prescribing information ([Section 15.1](#)) including:
 - a. G6PD deficiency
 - b. Breastfeeding
 - c. Psychotic disorder or current psychotic symptoms
 - d. Known hypersensitivity reaction to TQ
- (2) Evidence of severe or critical illness, defined by at least one of the following:
 - a. Clinical signs indicative of severe systemic illness with COVID-19, such as respiratory rate ≥ 30 breaths per minute, heart rate ≥ 125 beats per minute, $\text{SpO}_2 \leq 93\%$ on room air
 - b. Respiratory failure defined based on resource utilization requiring at least one of the following:
 - i. Endotracheal intubation and mechanical ventilation, oxygen delivered by high flow nasal cannula (heated, humidified, oxygen delivered via reinforced nasal cannula at flow rates > 20 L/min with fraction of delivered oxygen ≥ 0.5),

noninvasive positive pressure ventilation, extracorporeal membrane oxygenation (ECMO), or clinical diagnosis of respiratory failure (i.e., clinical need for one of the preceding therapies, but preceding therapies not able to be administered in setting of resource limitation)

- ii. Shock (defined by systolic blood pressure < 90 mmHg, or diastolic blood pressure <60 mmHg or requiring vasopressors)
- iii. Multi-organ dysfunction/failure

(3) Any other clinically significant acute illness unrelated to COVID-19 within seven days prior to first study drug administration

(4) Receipt of any experimental treatment for COVID-19 (off-label, compassionate use, or study-related) within the 30 days prior to the time of the screening evaluation

(5) Any excluded concomitant medication as described in the ARAKODA package insert ([Section 15.1](#))

(6) Any COVID-19 symptoms which, in the opinion of the investigator, is suggestive of possible requirement to hospitalize within 48 hours of enrollment

(7) Positive pregnancy test

(8) Have been symptomatic for more than five days when the first dose would be administered

